- Net area under the curve (netAUC) of postprandial glucose as measured by CGM in the 6 hours following the start of first meal. netAUC (mg/dL*min) will be calculated using a trapezoidal method [76], which sums all CGM values in the 6 hour period following the meal above the starting glucose and subtracts CGM values below the starting glucose.
- Percent of time with sensed glucose <70 mg/dl
- Percent of time with sensed glucose between 70 – 140 mg/dl
- Mean sensed glucose
- Percent of time with sensed glucose <54 mg/dl
- Percent of time with sensed glucose >180 mg/dl
- Percent of time with sensed glucose >250 mg/dl
- Mean amount of insulin delivered (in units and units/kg)
- Mean amount of pramlintide delivered (in mcg and mcg/kg)
- Coefficient of variation
- LBGI
- HBGI
- Safety endpoints (over full study duration):
 - Adverse events
 - Number of adverse events probably or possibly associated with pramlintide administration (see ‘Causality Relationship’ below)
 - Baxter Retching Faces (BARF)/VAS scale for gastrointestinal issues after first and second meal, see Protocol Appendix D.
 - Mean duration of gastrointestinal issues after first and second meal as reported by participant on BARF/VAS scale, see Protocol Appendix D.
 - Episodes of carbohydrate intake to treat hypoglycemia (defined as 15g carbohydrate intake)
 - Episodes of hypoglycemia defined as CGM <70mg/dL for 10 minutes or more
 - Number of provider-administered insulin injections due to hyperglycemia

Study Type

This is a single-center, crossover trial designed to evaluate glucose outcomes of a fully closed-loop system with insulin+pramlintide dosed in response to meal detection as compared to an insulin alone fully closed loop system.

Study Population

Study population will be adults with type 1 diabetes, ages 18 – 70 years of age. Younger participants are excluded as it is appropriate to assess safety first in the over 18 year old population. We are targeting a total of 35 participants to complete the full study protocol.

[figure not shown]
Power Analysis

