A sample size of 35 participants provides 90% power to detect a standardized paired mean difference of 0.56 SD, or 80% power to detect a 0.49-SD difference with a two-sided test at the .05 level of significance. This is calculated using a paired t test to approximate a mixed model with treatment, period, and sequence effects. Data from a previous study [24] showed a 0.64-SD reduction with pramlintide in 4-hour postprandial AUC for participants with >40 U bolus insulin per day. We plan to recruit more than half of our study participants from this population and so we expect to observe a slightly smaller reduction in AUC.

Protocol Summary:

Participants will undergo two study visits to evaluate (1) insulin+pramlintide versus (2) insulin-only delivery strategies. The order of the visits will be randomized. Meal scenarios will be identical across all study arms. Participants will arrive at approximately 7:30 am for all visits, be monitored through the afternoon and discharged at approximately 8 pm. During each study visit, participants will wear Omnipod(s) to deliver insulin and/or pramlintide and a Dexcom G6 CGM to measure glucose and a Polar M600 to measure activity levels. See Figure 1 and 2 below.

Figure 1: Study flow diagram

Time	Activity	Hours post meal
7:30 AM	Begin closed loop study	0
8 AM	Breakfast	1
9 AM		2
10 AM		3
11 AM		4
12 PM		5
1 PM		6
2 PM	Lunch	1
3 PM		2
4 PM		3
5 PM		4
6 PM		5
7 PM		6
8 PM	Discharge	

Figure 2: Treatment visit timeline

Subject Criteria

Inclusion Criteria:

1. Diagnosis of type 1 diabetes mellitus for at least 1 year.
2. Participants 18 to 70 years of age.
3. Current use of an insulin pump for at least 3 months with stable insulin pump settings for >2 weeks. OR Current use of multiple day injection insulin therapy with stable doses for >2 weeks.
4. Uses a carbohydrate ratio, at least occasionally, to dose meal time insulin
5. HbA1c \leq 10.5% at screening.
6. Total daily insulin requirement is less than 139 units/day.
7. Willingness to follow all study procedures, including attending all clinic visits.
8. Willingness to sign informed consent and HIPAA documents.

Exclusion Criteria:

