Participants will be asked to check glucose from CGM at 2am each morning before their treatment visit. If the CGM value is above 150 mg/dl, participants will be asked to take 80% of the correction bolus. If the glucose is less than 100 mg/dL they will be instructed to take 15 grams of carbohydrate. The participant will be asked to check his/her glucose before driving to the clinic and to bring a snack in the car in case hypoglycemia does occur (in which case, the participant must park and treat the hypoglycemia). After the first treatment visit, the washout period will be at least 3 days calculated from the day of admission until the start of the next admission. After arrival, women of childbearing potential will receive a urine pregnancy test if the last pregnancy test was more than 7 days prior. This test must be negative before further participation is allowed.

An assessment will take place at the beginning of each of the participant's closed-loop studies. We will inquire whether the participant has had changes in their medications and/or medical history to confirm the participant hasn't developed any study exclusion criteria. A CBG will be obtained and measured by a Contour Next glucose meter. When they arrive, participants will be given 15 grams of oral carbohydrate if the CBG reading is less than 70 mg/dl. CBG values > 300 mg/dl will be managed at the discretion of the investigator with a correction bolus and serum ketones will be checked. If serum ketones are >0.6 mM, the study will not be started and insulin therapy will be guided by the onsite investigator. The order of the visits will be randomized.

An Omnipod will be filled with aspart insulin. We will use only name brand insulin, not generic insulin. The Omnipod will be primed and inserted into the skin of the participant's abdomen or flank as directed by the manufacturer through the iPancreas smart phone application on a provided study phone. If applicable, participants will disconnect his/her own pump and remove his/her own insulin infusion set once insulin delivery has started via the Omnipod. If, applicable for participants on multiple daily injection therapy at baseline, we will verify time of last long

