Participants who will be taking an NPH dose prior to discharge from the clinic and who currently do not use a CGM or are not actively using their personal CGM will continue to use the study CGM for approximately 12 hours after the visit completes. Study staff will complete a phone check-in the next day to remove the CGM. For safety for avoiding hypoglycemia, all participants who take NPH prior to discharge will be asked to check glucose from CGM at 2am the morning after their treatment visit, if the glucose is less than 100 mg/dL they will be instructed to take 15 grams of carbohydrate. If the CGM value is above 150 mg/dL, participants will be asked to take 80% of the correction bolus.

Participants will be given a snack to take with them for the trip home. Participants will also be advised to monitor their glucose for any symptoms of hyperglycemia or hypoglycemia, before their next meal, and at bedtime.

Insulin + Pramlintide Treatment Visit

Participants will be asked to check glucose from CGM at 2am each morning before their treatment visit. If the CGM value is above 150 mg/dl, participants will be asked to take 80% of the correction bolus. If the glucose is less than 100 mg/dL they will be instructed to take 15 grams of carbohydrate. The participant will be asked to check his/her glucose before driving to the clinic and to bring a snack in the car in case hypoglycemia does occur (in which case, the participant must park and treat the hypoglycemia). After the first treatment visit, the washout period will be at least 3 days calculated from the day of admission until the start of the next admission. After arrival, women of childbearing potential will receive a urine pregnancy test if the last pregnancy test was more than 7 days prior. This test must be negative before further participation is allowed.

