Participants who will be taking an NPH dose prior to discharge from the clinic and who currently do not use a CGM or are not actively using their personal CGM will continue to use the study CGM for approximately 12 hours after the visit completes. Study staff will complete a phone check-in the next day to remove the CGM. The participants will be asked to check glucose from CGM at 2am the morning after their treatment visit. If the CGM value is above 150 mg/dl, participants will be asked to take 80% of the correction bolus. If the glucose is less than 100 mg/dL they will be instructed to take 15 grams of carbohydrate.

Participants will be given a snack to take with them for the trip home. Participants will also be advised to monitor their glucose for any symptoms of hyperglycemia or hypoglycemia, before

their next meal, and at bedtime. Study staff will call the participant approximately 1 hour after discharge and participant will obtain a fingerstick glucose at that time.

If a study visit is stopped prematurely, such as due to technical problems, the participant will be asked if they can repeat the study visit that was terminated early with additional compensation provided. Repeating the study visit will be optional.

Adverse Events

Causality relationship to Pramlintide administration

The causality of each AE should be assessed by the Investigator according to the following classification:

Probable: Good reason and sufficient documentation to assume a causal relationship.

Possible: A causal relationship is conceivable and cannot be dismissed.

Unlikely: The event is most likely related to etiology other than the pramlintide administration.

Not related: The event occurs before any pramlintide has been started.

Table 1: Schedule of Events

Automated insulin delivery system abbreviated AID

¹ ins/pram visit

	Screening	Active Treatment		End of Treatment
Description of visit procedures	Screening visit	Dexcom CGM insertion visit	1st AID visit	2nd AID visit
Visit Number	1	2	3	4
Visit Window		1-84 days	1-8 days	3-28 days
Informed Consent	X			
Medical history/	X	X	X	X
Focused physical	X			
Eligibility assessment	X			
Download data from participant's existing insulin pump and glucose sensor (if applicable)	X			
Review medications and doses	X	X	X	X
Hypoglycemia awareness survey	X			
Measure BP, pulse, height and weight	X			
Pregnancy Test (Urine)	X	X	X	X
Hemoglobin A1c	X			
Complete Blood Count (CBC)	X			
Comprehensive Metabolic Panel (CMP)	X			

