Adverse Event Reporting		X	X	X
Dexcom G6 CGM and iPancreas usage training		X		
Examination of sensor site after removal (if applicable)			X	X

Hypoglycemia Treatment Guidelines**CBG < 70 mg/dl**

- Give 15 grams of oral carbohydrate.

- Repeat treatment every 15 minutes as needed to raise blood glucose ≥ 70 mg/dl.
 - o If CBG < 70 mg/dL occurs during pramlintide treatment visit:
 - Give 15 grams of oral carbohydrate.
 - Repeat treatment every 15 minutes with 15 grams oral carbohydrate as needed to raise blood glucose ≥ 70 mg/dl.
 - Repeat CBG checks every 15 minutes for 45 minutes to ensure glucose is persistently ≥ 70 mg/dl.

Presence of STUPOR, LOSS OF CONSCIOUSNESS, or SEIZURE

- Give 3 mg glucagon intranasal
- Verify that insulin and pramlintide are turned off.

Hyperglycemia Treatment Guidelines

If the sensed glucose is ≥ 300 mg/dl, the participant will be instructed to check their blood glucose and to check the Omnipod for malfunction. This would include checking for insulin leaks, making sure Omnipod is securely adhered to skin, and check for error messages on the phone running the algorithm.

If capillary blood glucose value is over 300 mg/dl for more than 2 hours or is ≥ 400 mg/dl at any time, the participant will be instructed to check serum ketones using the Abbott Precision Xtra meter and to change out the Omnipod. If serum ketones are over 0.6 mM, the participant will be instructed by study investigator to discuss proper management, including delivering a correction bolus. In addition, the participant will be encouraged to drink sugar-free liquids. If serum ketones are above 1.5 mM at any time, the study will be stopped and insulin will be administered as directed by the on call investigator.

Cleaning and Disinfecting

All devices will be cleaned and disinfected between participants. The smart phone, Polar watch and Omnipod PDMs are cleaned by study staff. Technicians who are disinfecting units will wash hands thoroughly and wear gloves. All items will undergo intermediate-level disinfection using Oxivir TB disposable wipes. The disinfectant will be applied and allowed to air dry. After disinfection, when the units are completely dry, they will be placed in a sealed bag labeled with participant information.

Stopping Rules

Individual study stopping rules

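### No adverse event collection is scheduled after Visit 4, and the 1-hour call follows only the pramlintide visit, so post-discharge ascertainment depends on visit order

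*Combined protocol and SAP*

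**What the plan says.** **Schedule.** In Table 1 the row "Adverse Event Reporting" is marked at Visits 2, 3 and 4. Visit 4 is the second closed-loop visit and stands under the end-of-treatment heading. No column follows it, and no end date for AE collection is given elsewhere.

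**Order and timing.** The Protocol Summary states: "The order of the visits will be randomized". Participants will "be monitored through the afternoon and discharged at approximately 8 pm". Between visits, "the washout period will be at least 3 days calculated from the day of admission until the start of the next admission". Table 1 gives Visit 4 a window of 3-28 days.

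**Contact after discharge.** The insulin + pramlintide discharge section ends with: "Study staff will call the participant approximately 1 hour after discharge and participant will obtain a fingerstick glucose at that time". The matching insulin paragraph ends with advice only: "Participants will also be advised to monitor their glucose for any symptoms of hyperglycemia or hypoglycemia", before the next meal and at bedtime. Both discharge sections contain the line "Study staff will complete a phone check-in the next day to remove the CGM", limited to participants who take NPH before leaving and do not use, or are not actively using, their own CGM. Both also provide a return visit 1-3 days later if site inflammation reaches 1 cm.

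**Endpoints.** Safety is part of the first primary objective. The safety endpoints cover the full study duration and include all adverse events and "Number of adverse events probably or possibly associated with pramlintide administration".

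**Reporting.** Monitoring Procedures requires any AE to go to the monitor at once. Glucose excursions count as AEs only with ketones or with symptoms such as loss of consciousness or slurred speech.

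**The concern.** The protocol itself treats the hours after discharge as a period of risk. At the pramlintide visit the investigator considers pramlintide still on board. Some participants keep the study CGM for about 12 hours, and a 2 am glucose check is requested after the visit. However, no text has the 2 am value reported to staff, and the nausea scale looks back only over the 6 hours after each meal. Vomiting, a symptomatic low or a hospital attendance on the night after Visit 4 would, for most participants, reach the trial only if the participant volunteered it.

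Two things are at stake. The first is completeness: AE counts serve a primary safety objective, and one severe hypoglycemic event halts the whole study under the entire-study stopping rules. The second is comparability: one arm has an extra contact, and in one visit order the insulin visit's follow-up includes days on pramlintide.

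**Working it through.** The plan states no figure to reproduce here. The check sets the two discharge sections against Table 1 and works out the time to the next scheduled AE collection.

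**Inputs.** Discharge about 20:00 and arrival about 07:30 (Protocol Summary). Visit 4 window 3-28 days (Table 1), assumed to count from Visit 3, which agrees with the 3-day minimum washout. Run-in of three days before the pramlintide visit only (Run-in Period). Target of 35 completers.

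**Step 1: time from a Visit 3 discharge to Visit 4.** Arrival at 07:30 to discharge at 20:00 is 12.5 h, so hours = 24 × days − 12.5.
- 3 days: 72 − 12.5 = 59.5 h, about 2.5 days.
- 28 days: 672 − 12.5 = 659.5 h, about 27.5 days.

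**Step 2: the four cases.** The next-day check-in for the NPH subset applies equally in all four and is left out of the table.

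| Visit | 1-hour call | Next scheduled AE collection | Run-in inside the interval |
|---|---|---|---|
| Insulin, first | No | Visit 4, 3-28 days | Yes |
| Pramlintide, first | Yes | Visit 4, 3-28 days | No |
| Insulin, last | No | None | No |
| Pramlintide, last | Yes | None | No |

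Down the table, the length of follow-up changes with order and not with arm. Within an order position, the arms differ by the 1-hour call and, for first visits, by the run-in.

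**Step 3: how much of the insulin-first interval is run-in.** Run-in-free days = interval − 3.
- 3-day interval: 3 − 3 = 0 days.
- 28-day interval: 28 − 3 = 25 days.

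At the minimum interval, the insulin visit has no post-visit time clear of pramlintide. No rule says to which arm an AE in those days belongs.

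**Step 4: how many participants.** The allocation ratio is not stated. If order is 1:1, 35 / 2 = 17.5, so 17 or 18 participants end on each treatment. Some of these fall in the NPH subset, whose size is not given.

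**Step 5: size of the loss.** Let p be the share of an arm's visit-related AEs that begin after the last scheduled contact following a Visit 4 discharge. If order is 1:1, if Visit 4 captures everything after Visit 3, and if nobody reports spontaneously after Visit 4, the share missed is p × 1/2. With p = 20%, that is 10%. The documents give no p. Over p = 0 to 1 the result runs from 0 to one half, and it is an upper limit because the check-in subset and spontaneous reports recover some events. It bears on both arms about equally.

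**The case against.** The strongest reply is that the gap is narrow and does not favour an arm.

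- **A reader might infer that nobody is called after the insulin visit.** The documents do not support that. The same next-day check-in and the same conditional return visit for site inflammation stand in both arms. What remains is that the check-in reaches a subset and is described as serving CGM removal.
- **A reader might infer that overnight events after Visit 4 are lost.** That is too strong. Table 1 is a visit schedule and does not forbid recording AEs between visits, and Monitoring Procedures covers any AE that becomes known. Severe hypoglycemia, which by definition needs another person's help, is likely to come to light. Ordinary lows would not be AEs. But the reporting rule governs known events and creates no question or contact.
- **A reader might infer that unequal follow-up length biases the arm comparison.** Randomized order largely removes this, since each arm comes first in some participants and last in others. The objection stands on that point.
- **The 1-hour call asks for a fingerstick, not for AEs.** True as written. It is still a conversation with staff that only one arm has, so symptoms have one more chance to be mentioned.
- **No AE comparison by arm is specified, and causality is rated against pramlintide.** Statistical methods describes tests of the primary outcomes only, and the causality scale should assign much run-in nausea to pramlintide. This limits the harm for the pramlintide-associated count. It does not settle the count of all AEs.
- **The safety period may end at discharge.** The discharge sections speak of terminating the study at that point. AE marks at Visit 2 make that reading uncertain, and the ambiguity is itself a reason to state the end point.

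**Conclusion.** The point holds as a gap in ascertainment, not as a demonstrated bias. Scheduled AE follow-up after discharge is 3-28 days for the first treatment visit. For the second it is about 1 hour (pramlintide last) or nil (insulin last), except in the NPH subset. Two features differ by arm: the 1-hour call, and the run-in inside the insulin-first interval.

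This rests on reading the Visit 4 window as counted from Visit 3. The phrase most participants assumes that the NPH subset is a minority, since its size is not stated. The number of missed events cannot be derived from the documents. The consequence is confined to AE counts. Both primary endpoints come from CGM in the 6 hours after the first meal and are untouched. The change is worth making because safety is a primary objective and the remedy is cheap. It is not a reason to doubt the efficacy analysis.

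**What to change.** 1. Extend the existing next-day phone check-in to every participant after both treatment visits, with the same scripted AE question each time.
2. Add that call to Table 1 as the last AE collection point, so that the safety period has a stated end.
3. Tabulate AEs separately for run-in, treatment visit, and discharge to next-day call. Compare arms only on the visit and the matched post-visit period. List later between-visit events and run-in events without an arm comparison.

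The 1-hour call can stay as it is: once both arms are asked the same question the next day, an event first mentioned in that call falls in a period covered for both.

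Cost: at most 35 × 2 = 70 short calls for the target completers, some of which are already planned, made by existing staff, plus one line in Table 1 and a few sentences on AE tables. The downside is that a few more minor events will be recorded. No dose or clinical rule changes.
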